### 6.8.1 Multiple Assessments for the Same Assessment Time Point

In the case of multiple observations (e.g., scheduled vs. unscheduled) at a specific visit, the first non-missing measurement will be used for analysis, unless multiple study assessments are expected (e.g., pre-dose vs. post-dose). When multiple study assessments are expected, the first non-missing measurement for the visit and assessment time point will be used for analysis.

## 7. Subject Accountability

### 7.1 Subject Characteristics

Subject characteristics will be summarized by treatment group based on the FAS, which consist of all subjects who received at least one non-zero dose of study treatment.

*Demography.* Data collected about the following subject characteristics at the screening visit will be summarized:

- Age (in years). Age will be calculated as the number of years elapsed between birth date and the date of the screening visit.

Pfizer Inc. / Protocol: TTI-621-03/C4961003  
IQVIA Biotech (Confidential) Project # YXA42460

- Age strata:
  - < 40
  - 40 - < 65 years
  - 65 - <75 years
  - 75 - <85 years
  - ≥ 85 years
- Sex
- Race. If more than one race selected, summarize race as multiple.
- Ethnicity
- Height (cm)
- Weight (kg)
- Body Surface Area (BSA) (m^2) = ([height (cm) × weight (kg)] / 3600)0.5

*Medical History.* Medical Histories will be summarized as the numbers and percentages of subjects with histories significant for each of the medical-history elements recorded on the MH CRF form. Coding will be performed using Medical Dictionary for Regulatory Activities (MedDRA), latest version. System Organ Class (SOC) and Preferred Term (PT) will be summarized by number and percentage of patients having at least one occurrence of a disease. All Medical history information, including diagnosis and start/end date will be listed for the FAS.

*Disease Characteristics.* Disease characteristics will be summarized as the numbers and percentages of subjects with significant medical-history elements recorded on the Disease History CRF form, and target tumor sites at baseline from disease assessment CRFs. Disease History information, including histology information, stages, progressive disease date of most recent progression, and target tumor site will be listed.

*Prior anti-cancer therapies.* The prior anti-cancer therapies are collected under the 'Prior Treatment for Disease Under Study' and 'Prior Surgeries for Current Diagnosis' eCRF pages.

The number and percentage of participants in each of the following anti-cancer therapy categories will be tabulated:

- Participants with at least one prior anti-cancer drug therapy
- Participants with at least one prior anti-cancer surgery

Prior anti-cancer drug therapy will be summarized as follows based on the number and percentage of participants with the following:

- One prior anti-cancer drug therapy
- Two prior anti-cancer drug therapy regimens

Pfizer Inc. / Protocol: TTI-621-03/C4961003  
IQVIA Biotech (Confidential) Project # YXA42460

- Best response for each regimen: CR, PR, SD, PD, Unknown, Not applicable.

Prior treatment regimens can include Docetaxel, Gemcitabine, or/and other. If the starting date for Docetaxel and Gemcitabine and other anti-cancer drugs is the same or occurred within 14 days, these two treatments are considered as part of the same regimen.

*Concomitant Medication.* Concomitant medication is defined as any medication with a start date prior to the date of the first dose of study treatment and continuing after the first dose of study treatment or with a start date between the dates of the first and last dose of study treatment. Any medication with a start date after the date of the last dose of study treatment will not be considered a concomitant medication. Any medication with a stop date prior to the first dose of study treatment is defined as a prior treatment.

All concomitant medications and dietary supplements received within 28 days prior to the first dose of study treatment through 30 days after the last dose of study treatment will be recorded in the eCRFs, using generic drug names when possible. Concomitant medications will be coded using the WHO-DD current version and will be summarized by the 2nd ATC level and by preferred drug name of the coded medication. Patients are counted only once in each therapeutic class category. Concomitant medication will be summarized using the FAS and be tabulated for each dose level using frequencies and percentages. Percentages will be based on the number of patients in each dose level.

## 7.2 Disposition

The percentages below will be calculated based on the number of patients in the FAS.

End of Treatment (EOT): Subject's status (completed treatment [for doxorubicin only] or discontinued treatment), as well as the reasons for discontinuation of each study drug (Doxorubicin and PF-07901800 captured on separated forms) will be summarized.

End of Study (EOS): Subjects who discontinued or withdrew from the study, as well as the reasons, will be summarized.

All disposition data will be presented in a listing.

### 7.3 Protocol Deviations

A listing will identify subjects who were enrolled even though they did not meet one or more eligibility criteria (Data recorded in the EOS eCRF page), or any other situations that were not compliant with the protocol. This data will be classified as major or minor deviation by the clinical team, that will review periodically the protocol deviations and finalize the deviations prior to the database lock and efficacy analyses.

A summary table of major protocol deviations will be provided. A listing of protocol deviations related to COVID-19 will also be provided.

## 8. Efficacy Analyses

Efficacy analyses will use data from the FAS (for all efficacy endpoints) and will be descriptive in nature. Summary tables and figures will be presented by treatment group as described in Section 6.1, as applicable.

### 8.1 Efficacy Outcomes

For the primary endpoint, the clinical efficacy of PF-07901800 in combination with doxorubicin will be evaluated by tumor response as assessed by the investigators using RECIST v1.1, according to protocol appendix B (Eisenhauer, 2009).

The response categories of target lesions and its definitions are described below:

Complete Response (CR)	Disappearance of all target lesions. Any pathological lymph nodes (whether target or non-target) must have reduction in short axis to < 10 mm.
Partial Response (PR)	At least a 30% decrease in the sum of the longest diameter (LD) of target lesions, taking as reference the baseline sum LD.
Stable Disease (SD)	Neither sufficient shrinkage to qualify for partial response nor sufficient increase to qualify for PD, taking as reference the smallest sum LD since the treatment started.
Progressive Disease (PD)	At least a 20% increase in the sum of the LD of target lesions, taking as reference the smallest sum on study (this includes the baseline sum if that is the smallest on study). In addition to the relative increase of 20%, the sum must also demonstrate an absolute increase of at least 5 mm. The appearance of one or more new lesions is also considered PD.

Not Evaluable (NE)	No imaging/measurement is done at all at a particular time point. If only a subset of lesion measurements is made at an assessment, usually the case is also considered NE at that time point, unless a convincing argument can be made that the contribution of the individual missing lesion(s) would not change the assigned time point response, which is most likely to occur in the case of PD.
---------------------------	---

The response categories of non-target lesions and its definitions are described below:

Complete Response (CR)	Disappearance of all non-target lesions and normalization of tumor marker level.
Stable Disease/ Incomplete Response (Non-CR/Non-PD)	Persistence of one or more non-target lesion(s) or/and maintenance of tumor marker level above the normal limits.
Progressive Disease (PD)	Appearance of one or more new lesions and/or unequivocal progression of existing non-target lesions.

Best overall response (BOR) will be assessed based on reported overall lesion responses at different evaluation time points from the date of first study treatment until the first documentation of PD, according to the following rules. Only tumor assessments performed on or before the start date of any subsequent anti-cancer therapies (from the "Survival Status" eCRF) will be considered in the assessment of BOR. Clinical deterioration will not be considered as documentation of disease progression.

BOR based on confirmed responses (primary definition):

*Best Overall Response (BOR)* is defined as the best response recorded (CR, PR, SD, PD, NE per RECIST) from the start of the treatment until disease progression, taking as reference for PD the smallest measurements recorded since the treatment started. The patient's best response assignment will depend on the achievement of both measurement and confirmation criteria.

The tumor responses are required to be confirmed by radiographic tumor assessments. If an initial CR or PR is noted, confirmatory scans must be performed at least 4 weeks later. In the case of SD, follow-up measurements must have met the SD criteria at least once after study entry at a minimum interval of no less than 4 weeks.

Pfizer Inc. / Protocol: TTI-621-03/C4961003  
IQVIA Biotech (Confidential) Project # YXA42460

- CR = at least two determinations of CR at least 4 weeks apart and before first documentation of PD.
- PR = at least two determinations of PR or better (PR followed by PR or PR followed by CR) at least 4 weeks apart and before first documentation of PD (and not qualifying for a CR).
- SD (applicable only to patients with measurable disease at baseline) = at least one SD assessment (or better)  $\geq 4$  weeks after the date of first study treatment and before first documentation of PD (and not qualifying for CR or PR).
- Non-CR/non-PD (applicable only to patients with non-measurable disease at baseline) = at least one non-CR/non-PD assessment (or better)  $\geq 4$  weeks after the date of first study treatment and before first documentation of PD (and not qualifying for CR or PR).
- PD = first documentation of PD  $\leq 12$  weeks after the date of first study treatment (and not qualifying for CR, PR, SD or non-CR/non-PD4)
- NE: all other cases.

Objective Response (OR) is defined as confirmed BOR of CR or PR according to RECIST v1.1. OR rate (ORR) is the proportion of patients with OR in the analysis set.

BOR based on unconfirmed responses (secondary definition):

- Unconfirmed CR (uCR) = one objective status of CR before first documentation of PD.
- Unconfirmed PR (uPR) = one objective status of PR before first documentation of PD (and not qualifying for uCR).
- SD (applicable only to patients with measurable disease at baseline) = at least one SD assessment (or better)  $\geq 4$  weeks after the date of first study treatment and before first documentation of PD (and not qualifying for uCR or uPR).
- Non-uCR/non-PD (applicable only to patients with non-measurable disease at baseline) = at least one non-uCR/non-PD assessment (or better)  $\geq 4$  weeks after the date of first study treatment and before first

Pfizer Inc. / Protocol: TTI-621-03/C4961003  
IQVIA Biotech (Confidential) Project # YXA42460

documentation of PD (and not qualifying for uCR or uPR).

- PD = first documentation of PD  $\leq$  12 weeks after the date of or first study treatment (and not qualifying for uCR, uPR, SD or non-CR/non-PD).
- NE: all other cases.

An objective status of uPR or SD cannot follow one of uCR. SD can follow uPR only in the rare case that tumor increases by less than 20% from the nadir, but enough that a previously documented 30% decrease from baseline no longer holds.

Unconfirmed Objective Response (uOR) is defined as unconfirmed BOR (uBOR) of uCR or uPR according to RECIST v1.1. Unconfirmed OR rate (uORR) is the proportion of patients with uOR in the analysis set.

## 8.2 Primary Efficacy Outcome Analysis

Baseline documentation of “target” and “non-target” lesions (lesion count and maximum lesion length) will be recorded in listings. The sum of diameters will be calculated for all target lesions at baseline and at each subsequent tumor assessment as a measure of tumor burden. The baseline lesion size value will be used as reference by which to characterize the lesion response.

Other lesions (or sites of disease) not selected as target lesions (measurable or non-measurable), including pathological lymph nodes, should be identified as non-target lesions and should also be recorded during screening. Measurements of these lesions are not recorded, but the presence or absence of each, including any progression, should be noted throughout the study. The appearance of new malignant lesions denotes disease progression.

Per RECIST criteria, target lesions considered ‘too small to measure’ will be assigned a default value of 5 mm and those identified as ‘not present’ will be assigned 0 mm for purposes of analysis.

All FAS patients will be included in the denominators for percentage, even if the patient had a NE response. The ORR and uORR will be summarized descriptively for RECIST assessment method, with a 95% confidence interval (CI) using Wilson’s score method.

Overall tumor response assessment data will be presented in listings.

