***Disease Characteristics***

5. Histologically-confirmed high-grade soft tissue sarcoma that is metastatic or locally advanced and not amenable to curative treatment with surgery or radiation
  - In the dose escalation portion of the study, indications will be limited to high-grade leiomyosarcoma, undifferentiated pleomorphic sarcoma, myxofibrosarcoma, dedifferentiated liposarcoma, angiosarcoma and epithelioid sarcoma
  - In the expansion portion of the study, enrollment will be restricted to high-grade leiomyosarcoma that is histologically-confirmed at a central laboratory. The patient may be enrolled based on a current or most recent pathology report that provides sufficient detail to support derivation of the histologic interpretation but a pre-treatment tissue specimen must be made available for confirmation during screening or within the first cycle of treatment
6. Objective evidence of disease progression unless disease is newly-diagnosed
7. Measurable disease per RECIST v1.1 (expansion cohorts); target lesions must not be chosen from a previously-irradiated field unless there has been radiographically and/or pathologically documented tumor progression in that lesion prior to enrollment

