**12.3.3. Clinical Benefit**

Clinical efficacy will be evaluated by tumor response for patients with measurable disease as assessed by the Investigators using RECIST v1.1 (Appendix B). Duration of response will be calculated for patients who achieve a CR or PR and is defined as the time from the date of first documented response (CR or

PR) to the date of documented progression or death after achieving response. Disease control rate is defined as the percentage of patients who have achieved CR, PR, or SD lasting at least 12 weeks.

Clinical activity based on CCI [REDACTED] will be assessed as an CCI [REDACTED] of the study.

Patients enrolled in an expansion cohort who withdraw from the study prior to the first objective disease assessment for a reason other than disease progression or safety will be replaced in order to meet the statistical criteria for the Simon two-stage design; these patients will not be included in the response-evaluable population. For a patient enrolled into the dose expansion portion of the study based on local pathology that is not confirmed during central review, the patient must be replaced for purposes of meeting the statistical requirements of the study but may be allowed to continue on treatment after discussion with the Sponsor Medical Monitor.

For patients with asymptomatic progression only or suspected pseudoprogression, the patient may continue treatment beyond progression until a confirmation scan at least four weeks later has confirmed progression.

Efficacy analyses will be based on the efficacy analysis population, i.e. all patients who received at least one dose of study treatment, unless otherwise specified.

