## 6.7 Analysis Populations

### 6.7.1 Full Analysis Set (FAS)

The FAS will include patients who were enrolled, allocated to treatment, and received at least one non-zero dose of study treatment.

This analysis population will be used for baseline summaries and the analysis of efficacy endpoints.

Patients will be classified according to the study treatment actually received. For patients who received a wrong study dose, they would be recoded in protocol deviation and dosing compliance; if the wrong dose occurred only once, the analysis will use the patients' initial planned dose as summary cohorts. If more than one wrong dose occurred, the analysis will use patients' actual dose as summary cohorts. If patients' doses were reduced, safety analysis will use the initial planned dose as summary cohorts. Patients receiving different dosing schedules will be presented in the listings only.

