### 8.3 Secondary Efficacy Analyses

*Duration of response (DOR)* will be calculated for patients who achieve a CR or PR, and is defined as the time from the date of first documented response (CR or PR) to the date of documented progression or death of any cause after achieving response. Patients who discontinue the study without disease progression or death or patients with an event after 2 or more missing/inadequate disease assessment or patients with an event after the start date of alternate anti-cancer therapy will be censored at their last response assessment date or last assessment prior to the start date of alternate anti-cancer therapy, whichever is earlier. The number of events and the number of censored patients will be summarized, and the median time to PD or death event (reported in days), its 95% confidence interval, and the 25th and 75th percentiles on the time to event will be summarized using Brookmeyer-Crowley method.

*Disease Control Rate (DCR)* is defined as the percentage of patients who have achieved CR, PR, or SD lasting at least 4 weeks. DCR at any time during the study will be summarized, as per the RECIST assessment method.

*Progression Free Survival (PFS)* is defined as the time from the first PF-07901800 infusion (Cycle 1 Day 1) to PD or death of any cause, whichever is first. Patients without disease progression or death or patients with an event after 2 or more missing/inadequate disease assessment or patients with an event after the start date of alternate anti-cancer therapy will be censored at their last response assessment date or last assessment prior to the start date of alternate anti-cancer therapy, whichever is earlier.

The number of events and the number of censored patients will be summarized. PFS rate at selected times, as well as the median time to event (reported in days), its 95% confidence interval, and the 25th and 75th percentiles on the time to event will be summarized using Brookmeyer-Crowley method. Kaplan-Meier plot of PFS will also be provided.

*Overall Survival (OS)* is defined as the time from the first PF-07901800 infusion (Cycle 1 Day 1) to death of any cause. Patients last known to be alive will be censored at their last known alive date. Kaplan-Meier methodology similar to the PFS analysis will be used to summarize the results.

Pfizer Inc. / Protocol: TTI-621-03/C4961003  
IQVIA Biotech (Confidential) Project # YXA42460

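### DCR and duration of disease control leave out Non-CR/non-PD, so an escalation patient with stable non-measurable disease counts as a disease-control failure

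*SAP*

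**What the plan says.** **Who may enter.** Protocol Section 6.2, criterion 7, reads "Measurable disease per RECIST v1.1 (expansion cohorts" and so ties the requirement to the expansion phase. Protocol Section 5.1 says the same. The study-design text of the synopsis lists measurable disease without that limit, but the criterion itself carries it.

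**Who is analysed.** SAP Section 6.7.1: "The FAS will include patients who were enrolled, allocated to treatment, and received at least one non-zero dose of study treatment". It sets no condition on measurability. SAP Section 8: "Efficacy analyses will use data from the FAS (for all efficacy endpoints) and will be descriptive in nature". SAP Section 8.2 adds: "All FAS patients will be included in the denominators for percentage, even if the patient had a NE response". That sentence stands in the ORR section. DCR is covered by the Section 8 statement and by the general rule in SAP Section 6.8 that percentages are taken over the analysis population.

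**How response is classed.** In SAP Section 8.1, PR is defined on the sum of target-lesion diameters. The rule for SD begins "SD (applicable only to patients with measurable disease at baseline". Patients with non-measurable disease have their own category, Non-CR/non-PD, with the same four-week minimum.

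**What counts as disease control.** SAP Section 8.3 defines DCR as "the percentage of patients who have achieved CR, PR, or SD lasting at least 4 weeks". DDC is restricted to patients in the same three categories.

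**What is tabulated.** SAP Section 6.1 lists each escalation cohort, a Phase 1 total and pooled rows at 0.2 and 2.0 mg/kg. Only the total across both phases is barred from efficacy.

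**The concern.** The SAP creates Non-CR/non-PD as the counterpart of SD for patients without measurable disease, and then uses it in no rate or duration endpoint in Section 8.3. A patient whose non-measurable disease does not progress for a year scores in DCR exactly as one who progressed at the first scan, and contributes nothing to DDC. Nothing in the SAP suggests that this is intended. Counting NE patients in the denominator is a conservative rule for missing assessments. These patients are assessed and stable, but the category they fall into is not counted.

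At stake is a downward bias in the descriptive DCR for the dose-escalation rows. It extends to the pooled dose-level rows, where escalation and expansion patients are combined. DDC would describe a selected subset in the same rows.

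**Working it through.** **The plan's own figure.** The documents give no figure for DCR. The only design calculation is the Simon plan in SAP Section 4.3.2: 18 then 31 patients, continue with at least 2 responses, success with at least 5, rates of 10% and 25%. The probability of success is the sum over x from 2 to 18 of P(X1 = x | 18, p) × P(X2 ≥ 5 − x | 13, p). This gives 0.182 at p = 0.10 (ceiling 0.20) and 0.902 at p = 0.25 (stated 0.90). The plan reproduces. It concerns ORR in patients who must have measurable disease, so the point below does not touch it.

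**Categories open to a patient with only non-measurable disease**

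| Best overall response | Attainable? | Counts in DCR? | Enters DDC? |
|---|---|---|---|
| CR | yes | yes | yes |
| PR | no (needs target lesions) | – | – |
| SD | no (SAP 8.1) | – | – |
| Non-CR/non-PD | yes | no | no |
| PD or NE | yes | no | no |

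The table for non-target-only disease in Protocol Appendix B agrees: it offers CR, Non-CR/non-PD, NE and PD.

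**Size.** Let N be the patients in a row, d those with CR, PR or SD, and s those with Non-CR/non-PD of sufficient duration.

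- DCR as written = d/N.
- DCR with the category counted = (d + s)/N.
- Shortfall = s/N.

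*Example: N = 6, d = 3, s = 1.* As written, 3/6 = 50%. With the category counted, 4/6 = 67%.

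The Wilson 95% interval, which Protocol Section 12.4 specifies for DCR, is [p + z²/2N ± z√(p(1−p)/N + z²/4N²)] / (1 + z²/N) with z = 1.96. It gives about 19% to 81% for 3/6 and 30% to 90% for 4/6.

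*Range.* The documents do not give k, the number of patients with non-measurable disease in a row. Assume that 60% of all patients have disease control and that no non-measurable patient reaches CR. The expected DCR as written is then 0.60 × (N − k)/N, against 60% with the category counted.

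| Row | N | k = 0 | k = 1 | k = 3 | k = 6 |
|---|---|---|---|---|---|
| Pooled 0.2 mg/kg | 31 + 6 = 37 | 60% | 58.4% | 55.1% | 50.3% |
| Pooled 2.0 mg/kg | 18 + 6 = 24 | 60% | 57.5% | 52.5% | 45.0% |
| Phase 1 total | 18 | 60% | 56.7% | 50.0% | 40.0% |

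The escalation sizes are the planned maxima of six per dose level. For the 2.0 mg/kg row I use the 18 Cohort B patients described in SAP Section 4.3.2. SAP Section 6.1 attaches the 1.0 and 2.0 mg/kg labels to Cohorts B and C the other way round; here that would change only N.

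**The case against.** The best reply is that the exclusion is not certain. SAP Section 8.1 labels the non-target category as stable disease or incomplete response, with Non-CR/Non-PD in brackets, so a programmer might count it as SD. But that label grades non-target lesions. At the level of best overall response, which DCR and DDC use, the same section limits SD to measurable disease and gives the other patients a separate category. Followed as written, they are excluded. If the sponsor intended otherwise, the wording still needs the same correction.

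The second reply stands. Escalation is there to assess safety, these rows are descriptive, no decision depends on them, and the number of affected patients may be zero. In a cohort of six the shift is small beside the interval width.

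A reader might infer more, namely that the ORR denominator is also wrong and that the SAP departs from the protocol, because Protocol Section 12.3.3 opens with "Clinical efficacy will be evaluated by tumor response for patients with measurable disease as assessed by the Investigators using RECIST v1.1". The documents do not support that. Protocol Section 12.2 defines the efficacy population as all treated patients, and Section 12.3.3 ends by basing efficacy analyses on all treated patients unless otherwise specified. The opening sentence can equally describe the method of assessment. An all-treated ORR denominator is a defensible, conservative choice that the SAP states openly. Restricting it would also remove any non-measurable patient with a confirmed CR and would give the two phases different rules.

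**Conclusion.** The point holds for DCR and DDC, and is minor. As written, an escalation patient with stable non-measurable disease stays in the DCR denominator as a failure and is left out of DDC. The shortfall in DCR is s/N: 17 percentage points for one such patient in six, and zero if there are none. In the pooled rows, on the 60% assumption, three such patients cost 4.9 points at 0.2 mg/kg (60 − 55.1) and 7.5 points at 2.0 mg/kg (60 − 52.5). This applies only if those rows are used for efficacy, which SAP Sections 6.1 and 8 leave as applicable.

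Two stronger inferences fail. These patients are not failures by definition, because CR remains open to them. Nor is the Phase II result affected: the expansion cohorts require measurable disease, so their ORR and DCR and the Simon rule do not change.

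**What to change.** In SAP Section 8.3:

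- Define DCR as the percentage of FAS patients with CR, PR, SD or Non-CR/non-PD, with the minimum duration for SD applied equally to Non-CR/non-PD. The SAP sets that minimum at 4 weeks and Protocol Section 12.3.3 at 12 weeks; that difference is a separate matter.
- Define DDC in patients whose best overall response is CR, PR, SD or Non-CR/non-PD, on the same terms.

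In SAP Section 8.1, add Non-CR/non-PD to the list of best overall response values, which now omits it. Footnote the escalation and pooled rows with the number of patients who had no measurable disease at baseline. Leave the all-FAS denominator for ORR as it is.

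The cost is a few lines of SAP text and one derived flag. SAP Section 8.2 already has baseline target and non-target lesions recorded, so no new data are needed, and SAP Section 1.2 allows the efficacy plan to change before database lock. The one drawback is that DCR in these rows will combine measured stability with a qualitative judgement of stability; the footnote makes that visible.
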